### 6.2 Missing Data

In general, missing clinical data will not be imputed, except where explicitly defined. In the event of study withdrawal, a subject's final assessment will be used as the endpoint value, if applicable. For Trail Making Test A & B, if the assessment was not done due to cognitive reasons, the max score would be imputed. Note that the reason for "not-done" assessment is captured in the eCRF, and the specify field provides reason why. If the reason relates to cognitive reasons, the maximum time for Trails A (150 seconds) or for Trails B (300 seconds) is used.

Data are considered to be "on-treatment" if the assessment or collection follows the first administration of study medication and if the assessment occurs within 45 days following the final administration of study medication, justified based on the long half-life of this drug.

Dates with missing fields will not have days imputed.

In accordance with the recommendations of the report from the National Academy of Science (NAS) panel "*The Prevention and Treatment of Missing Data in Clinical Trials*," (National Research Council, 2010), sensitivity analyses will be done to ensure that study conclusions are robust against missing data. Last observation carried forward (LOCF) and baseline observation carried forward (BOCF) methods may be used as appropriate in sensitivity analysis. Missing data types will be examined, and statistical methodologies for appropriate sensitivity analyses will be finalized during blind data review as patterns emerge as the study progresses. Primary methodologies following the ITT principle are not subject to change.

The three types of missing data ([Rubin, 1976](#)) are considered to examine robustness of analysis conclusions against missingness and type of missingness:

- MCAR (missing completely at random) assumes the event of missingness is independent both of observable values and of unobservable values, and the missingness is entirely at random.
- MAR (missing at random) assumes that the missingness can be fully accommodated by accounting for variables where data are available.

- MNAR (missing not at random) the missingness may be related to the reason the data are missing.

The robustness of analysis conclusions against missingness is managed through supportive and sensitivity analyses, employing techniques MAR MI for placebo and MAR MI with delta adjustment (jump-to-placebo) for the group randomized to TTP488 (O’Kelly and Ratitch, *Clinical Trials with Missing Data: A Guide for Practitioners*, 2014).

### **6.3 Dropouts**

If a subject withdraws from the study, if the date of an adverse event is not available and a determination of whether or not the event is treatment emergent cannot be made, by convention the event will be considered to be treatment emergent.

### **6.4 Visit Windows**

Assessments taken outside of protocol allowable windows will be displayed according to the case report form (CRF) assessment recorded by the investigator.

### **6.5 Early Termination Assessments and Follow-up Assessments**

When a patient withdraws from the study prematurely for any reason, an early termination (ET) visit is to be performed, except in the case when a patient withdraws consent (and the protocol specifically states that no further data would be collected). An ET visit should be “on treatment,” and efficacy data collected at the ET visit are suitable for use in statistical analysis. Efficacy data from an ET visit will be mapped to a scheduled visit based on the study day of the ET visit using the convention that the ET is mapped to the nearest scheduled visit by date. If a subject has more than one efficacy value for a visit, the assessment closest to the target day for the visit will be used for analysis.

A follow-up visit is planned for subjects 3 months following the last dose of study medication, noting that subjects who roll-over into the open-label extension study will not have the follow-up visit, because the last day of dosing for TTP488-301 is one day before the planned first dose of medication under TTP488-303 (the protocol for the open-label extension study). Data collected at the follow-up visit are not considered “on treatment,” and the data are not suitable for use in statistical analysis (as the data can be tainted by other treatments).

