Upon completion of the study and locking the database, protocol-planned analysis of ADAS-cog data from 100% of subjects who were ongoing or who had completed 18 months at the time of study termination were performed. Analysis showed a beneficial effect of less cognitive decline in the 5 mg/day group compared to placebo at Month 18 ($\Delta = 3.1$, $p = 0.008$, analysis of covariance [ANCOVA] with multiple imputation). To confirm robustness of effect to statistical analysis procedures, this difference was found to be significant using other statistical models (ANCOVA with last observation carried forward [LOCF; $p = 0.03$] and generalized estimating equations [GEE; $p = 0.03$]).

Analysis was done to examine the impact of off-treatment data on analysis conclusions. Statistical analysis on ADAS-cog was performed using all available on-treatment data (“on treatment” defined as data collected within 45 days of the last

dose of study medication). Forty-five days was selected based on the long half-life of azeliragon (mean = 18 days in elderly participants) and the demonstration of measureable, appreciable concentrations during that time frame following the last dose. Mean changes in ADAS-cog show numerical active-placebo differences favoring the 5 mg/day dose group over time at all time points, with nominal significance at Month 18 (delta=2.7, p = 0.03).

The key secondary measure of CDR-sb at 18 months showed a numerical difference favoring 5 mg azeliragon over placebo CDR-sb (LOCF, delta = 0.73, p = 0.1)

The current study will enroll patients with mild Alzheimer's disease. Subgroup analyses of data in Study TTP488-203 based on baseline severity of AD (mild or moderate), planned in the protocol and SAP, showed a more pronounced benefit of treatment with azeliragon among subjects with mild disease (MMSE 21 or more). In patients with mild AD, the difference in ADAS-cog mean change from baseline at 18 months was 4.0 (p = 0.018). In addition, a nominally statistically significant difference in CDR-sb mean change from baseline was demonstrated (delta = 1, p = 0.02) when comparing azeliragon 5 mg + SoC with placebo + SoC at Month 18. Thus, in the Phase 2 trial statistically significant differences between azeliragon 5 mg/day and placebo on cognition and global performance (using USA FDA agreed upon Phase 3 registration measures of ADAS-cog and CDR-sb) have been demonstrated.

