9.6.2 Statistical Methodology for Safety Analysis

Adverse events will be coded using MedDRA Version 16.0 or above. Adverse event coding will be done to the lowest level term (LLT). All treated patients will be included in the assessment of safety. Adverse events will be summarized by MedDRA System Organ Class and Preferred Terms. Separate tabulations will be

produced for related AEs (those considered by the Investigator as drug related), SAEs, discontinuations due to AEs, and severe events.

Vital signs, ECG results, and laboratory data will be tabulated for changes over time on study. In addition, TEAV and significant findings will be summarized.

The following assessments are constructed to provide a view of safety assessments after more than one dose of study medication with variable exposure including assessments of change to worst value (to examine worse value, minimum and maximum values are examined):

- Baseline
- First on treatment
- Last on treatment
- Last available (includes off-treatment values and safety follow-up assessment values)
- Minimum value
- Maximum value

For each post-Baseline assessment, descriptive statistics are provided for the assessment value and the change from Baseline to the assessment.

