## 1.5 Study Design

This trial is a multi-center, randomized, double-blind, placebo-controlled, parallel-group study evaluating the efficacy and safety of 18 months of treatment with azeliragon relative to placebo conducted in approximately 800 mild AD patients who are on background standard of care (SoC). Patients will be randomly assigned to 1 dose level (5 mg/day plus SoC) or placebo plus SoC in a 1:1 randomization (approximately n=400/group).

This protocol describes two statistically independent studies with a common infrastructure. Statistical analysis for clinical efficacy will be analyzed as two identical separate studies (A-study and B-study). Analysis for safety and all secondary and exploratory endpoints will be analyzed for both the A and B study as a whole (i.e., the two studies combined).

A-study is conducted at multiple sites in the U.S and Canada.

B-study is conducted at multiple sites in the U.S., Canada, Ireland, UK, South Africa, New Zealand, and Australia.

The overall structure of the study includes the following periods:

**Screening period:** Screening procedures occur within 60 days of start of study drug administration, and they include obtaining informed consent and evaluations to determine eligibility for study participation.

**Baseline Study Period** (Day -7 — Day 1, pre-dose): Subjects will have baseline assessments for efficacy and safety measures, including vital signs, safety labs, adverse events, electrocardiography and concomitant medications, as well as imaging and PK/PD assessments.

**Treatment Period** (Day 1 — Month 18): Subjects are treated with double-blind study medication. Efficacy and safety measures are taken. Blood samples are taken and subjects have assessments for safety and PK.

**Follow-up period** (Month 21): Subjects return to the site for final safety assessments including vital signs, adverse events, electrocardiography and concomitant medications are taken. Blood draws are taken for safety evaluations and for pharmacokinetics evaluations.

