### 4.2.1 Treatment-emergent Adverse Events

Adverse events will be coded using Medical Dictionary for Regulatory Activities (MedDRA) Version 16.0 or above. Adverse event coding will be done to the lowest level term (LLT). Adverse events will be summarized by System Organ Class (SOC) and preferred terms (PT).

Definitions:

- A treatment-emergent adverse event (TEAE) is an event that is observed or reported after administration of study medication that was not present prior to study medication administration or an event that represents the exacerbation of a pre-existing event.
- An adverse withdrawal is a subject who withdrew from the study due to an adverse event.
- A serious adverse event (SAE) is an AE that is classified as serious according to the criteria specified in the study protocol.

Safety and tolerability variables based on adverse events include the following:

- Proportions of subjects with TEAEs by Preferred Term and decreasing frequency of AEs
- Proportions of subjects with TEAEs by System Organ Class and Preferred Term
- Proportions of subjects with related TEAEs
- Proportions of subjects with severe TEAEs
- Proportions of subjects who died.
- Proportions of subjects with treatment-emergent SAEs other than death.
- Subjects with TEAEs that result in study termination.

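### SAP 6.5 bars follow-up-visit data from statistical analysis without limiting the bar to efficacy, contradicting the SAP's own safety sections and Protocol 9.6.2

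*SAP*

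**What the plan says.** SAP 6.5 has two paragraphs. The first deals with the early termination (ET) visit and is worded for efficacy throughout: "efficacy data collected at the ET visit are suitable for use in statistical analysis", and the mapping and tie-breaking rules that follow also name efficacy values. The second deals with the follow-up visit: "A follow-up visit is planned for subjects 3 months following the last dose of study medication". It explains that "subjects who roll-over into the open-label extension study will not have the follow-up visit". It then classes all data from the visit as off treatment and concludes that "the data are not suitable for use in statistical analysis (as the data can be tainted by other treatments". No word restricts this to efficacy.

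Elsewhere the plan treats the same visit as a safety visit. SAP 1.5 says of it: "Subjects return to the site for final safety assessments including vital signs, adverse events, electrocardiography", with blood drawn for safety and PK. The schedule in SAP 12 places ECG, haematology, chemistry, urinalysis, blood pressure and pulse, C-SSRS and adverse-event assessment at Month 21.

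Protocol 9.6.2 lists the constructed assessments for the safety analysis. One of them is "Last available (includes off-treatment values and safety follow-up assessment values".

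**The concern.** The follow-up visit is where a patient is next seen, on schedule, after most of the drug has gone. In patients who stop early it can show whether an abnormal laboratory value or ECG has returned to normal, or whether a new one has appeared. A rule that bars its data from analysis would leave the safety summaries without that view.

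The reason given, contamination by other treatments, bears on efficacy scores. It is a weak reason to leave out safety values, which can simply be labelled off treatment, as Protocol 9.6.2 intends. At stake are the counts of treatment-emergent events and abnormal values, the QTc categories, and the by-visit safety summaries. Two competent programmers could produce different versions of these from the same SAP.

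**Working it through.** The documents give no figure on this point to reproduce. The check is a comparison of texts, plus one calculation on timing.

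**1. How far from the last dose is the visit?**

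Inputs:
- Half-life, Protocol 1.1.3: "azeliragon (mean = 18 days in elderly participants".
- Month 18 is Day 540 and Month 21 is Day 630, with a window of ±7 days (schedule of activities).
- The on-treatment limit is 45 days after the last dose (SAP 6.2, Protocol 9.11).

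Formula, assuming first-order elimination: residual fraction = 0.5^(days / 18).

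| Days after last dose | Half-lives | Residual drug |
|---|---|---|
| 45 (on-treatment limit) | 45/18 = 2.50 | 17.7% |
| 83 (early end of window) | 83/18 = 4.61 | 4.1% |
| 90 (630 − 540) | 90/18 = 5.00 | 3.1% |
| 97 (late end of window) | 97/18 = 5.39 | 2.4% |

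No other scheduled visit is placed this far from dosing. SAP 6.5 expects the ET visit to be on treatment.

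**2. Which text would remove the safety data, and which would keep it?**

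| Text | Effect on follow-up safety data |
|---|---|
| SAP 6.5, second paragraph | Removes it: no limit to efficacy |
| SAP 6, opening line | Applies the section's conventions to the statistical analysis generally |
| SAP 1.5 and 12 | Keeps it: the visit is described and scheduled as a safety visit |
| SAP 4.2.1 (TEAE) | Keeps it: "an event that is observed or reported after administration of study medication", with no end date |
| SAP 4.2.4 (TEAV) | Keeps it: abnormal after dosing, normal before, with no end date |
| SAP 5.4.2 and 5.4.3 | Keeps it: vital signs and laboratory values summarised at every post-baseline assessment |
| SAP 5.4.5 | Keeps it: ECG summarised at every scheduled time, which includes Month 21 |
| SAP 4.3 and 4.4 | Month 21 is named as a PK and plasma A-beta sampling time, although SAP 5.5 and 5.6 describe changes over the 18-month treatment period |
| Protocol 9.6.2 | Keeps it: a last-available summary that includes follow-up values |

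**3. Is there a rule that resolves the conflict?** Protocol 9.0 ranks the SAP above the protocol. That does not rank SAP 6.5 above SAP 4.2 or 5.4, and no text does.

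**4. Is the departure from Protocol 9.6.2 declared?** SAP 5.4 does not carry over the last-available assessment. SAP 1.9 declares one modification only, the removal of Bazett's correction.

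**5. What it means for one patient.** Suppose a patient stops early and has a normal ALT until a value above the SAP 10 threshold at the follow-up visit. Under SAP 4.2.4 this is a treatment-emergent abnormal value of potential clinical concern. Under SAP 6.5 read literally, it is not analysed.

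**The case against.** The strongest reply is that only efficacy was meant. The sentence follows a paragraph about which efficacy values are usable, the reason given suits efficacy scores, and a literal bar would contradict SAP 1.5, 4.3 and 4.4. This is probably what the authors intended. But SAP 6.1 and the first paragraph of 6.5 name safety or efficacy when they mean only one of them, and the follow-up sentence names neither. Nor can safety be exempted on the ground that it is only descriptive: SAP 5 places the descriptive safety summaries within its statistical methodology.

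Four stronger readings are tempting, and the documents do not support them:

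- *The data drop out of the safety analysis.* This is not established. SAP 4.2 and 5.4 would keep them, and SAP 9 plans listings of all adverse events, deaths and serious events.
- *The exclusion wins because the SAP supersedes the protocol.* That rule does not reach a conflict inside the SAP.
- *The SAP has also abandoned the protocol's minimum and maximum summaries.* SAP 5.4 does not repeat them, but SAP 6.6 still refers to minimum and maximum over time. The last-available summary is the clear omission.
- *Adverse events after stopping would be lost.* They are not tied to one visit. Protocol 8.2 runs serious-event reporting to Month 21, with suspected related events reported afterwards. Protocol 8.7 follows related events to resolution or loss to follow-up, and others to resolution or 60 days after participation ends. The adverse-event part of the point is therefore the weakest.

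**Conclusion.** The point holds as an unscoped sentence that contradicts other parts of the plan, together with an undeclared omission of a safety summary planned in the protocol. If SAP 6.5 is followed as written, the only scheduled near-washout laboratory, ECG, vital-sign and C-SSRS data leave the safety summaries. If SAP 4.2 and 5.4 are followed, they stay. The documents do not say which applies.

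The near-washout description rests on the mean half-life of 18 days and first-order elimination. It gives 3.1% residual drug at 90 days, or 2.4% to 4.1% across the visit window. Patients who eliminate the drug more slowly would retain more.

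The number of patients affected cannot be fixed from the documents, because they give no uptake for the extension. At the planning dropout rate of 20%, early discontinuers number at most 800 × 0.20 = 160, fewer once those who withdraw consent are removed. Completers due the visit could be anywhere from 0 to 800 − 160 = 640, depending on uptake.

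Sample size, power, alpha and the co-primary analysis are untouched. The correction should still be made, because it is cheap and safety counts should not depend on the section consulted.

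**What to change.** Keep the exclusion and limit it to efficacy. Suggested wording for the follow-up sentence in SAP 6.5:

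*Efficacy data collected at the follow-up visit are not considered on treatment and are not used in efficacy analyses, including LOCF and endpoint analyses.*

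Then add:

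*Adverse events, laboratory, ECG, vital-sign and C-SSRS data from the follow-up visit are included in the safety analyses, shown as an off-treatment time point.*

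The explicit exclusion should not simply be deleted. ADAS-cog and CDR are collected at follow-up (Protocol 6.2.10), the LOCF rule in SAP 5.2.1 takes the last measurement available, and SAP 6.2 uses a withdrawn patient's final assessment as the endpoint value. Neither rule is itself confined to on-treatment data, so the bar in SAP 6.5 is what keeps follow-up scores out.

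Restore the last-available safety summary of Protocol 9.6.2 in SAP 5.4, or list its removal in SAP 1.9.

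The cost is SAP wording and one extra column in existing safety tables. No new data are needed.

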### **6.6 Unscheduled Assessments**

Extra assessments (laboratory data or vital signs associated with non-protocol clinical visits or obtained in the course of investigating or managing adverse events) will be included in listings, but not summaries. If more than one laboratory value is available for a given visit, the observation identified by the investigator to be the scheduled assessment will be used in summaries; all observations will be presented in listings.

Data from unscheduled assessments will be included in longitudinal data summaries (e.g., minimum, maximum over time). Data planned at scheduled times for which unscheduled assessments are taken will not be reflected in by-visit summaries.

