7.1.5.2 Assessment of Potential Cases of Drug Induced Liver Injury

Abnormal values in aspartate transaminase (AST) and/or alanine transaminase (ALT) concurrent with abnormal elevations in total bilirubin that meet the criteria outlined below, in the absence of other causes of liver injury, are considered potential cases of drug-induced liver injury. These events should be considered important medical events, and reported as serious adverse events.

Participants who present with the following laboratory abnormalities should be evaluated further to definitively determine the etiology of the abnormal laboratory values:

- a. Participants with AST or ALT baseline values within the normal range who subsequently present with AST or ALT ≥ 3 times the upper limit of normal concurrent with a total bilirubin ≥ 2 times the upper limit of normal with no evidence of 1) hemolysis, 2) cholestasis (elevated alkaline phosphatase ≥ 2 times the upper limit of normal or not available) or 3) Gilbert's Syndrome (common benign condition associated with intermittent elevations of primarily indirect, unconjugated, bilirubin to about 2 X upper limit of normal.)
- b. Participants with pre-existing AST or ALT baseline values above the normal range who subsequently present with AST or ALT ≥ 2 times the baseline values and ≥ 3 times the upper limit of normal concurrent with a total bilirubin ≥ 2 times the upper limit of normal with no evidence of 1) hemolysis, 2) cholestasis (elevated alkaline phosphatase ≥ 2 times the upper limit of normal or not available) or 3) Gilbert's Syndrome (common benign condition associated with intermittent elevations of primarily indirect, unconjugated, bilirubin to about 2 X upper limit of normal.)

Increases defined above should be confirmed with repeat testing within 48 to 72 hours. In addition to repeating AST and ALT, laboratory tests should include albumin, amylase, creatine kinase, total bilirubin, direct and indirect bilirubin, gamma-glutamyl transferase (GGT), international normalized ratio (INR) and alkaline phosphatase. Symptoms should be assessed. The medical monitor should be contacted to discuss the patient's condition.

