#### **5.4.4 Liver Enzyme Function Tests**

Liver function tests have additional analysis views for this study in accordance with current regulatory guidance. To explore the potential for drug-induced liver injury consistent with *Guidance for Industry “Drug-induced liver injury: premarketing clinical evaluation”* ([CDER, CBER, July 2009](#)), subjects will be summarized and listed who meet the following criteria:

- (1) Elevations in either AST or ALT of at least 3-times the upper limit of normal, and
- (2) An accompanying abnormal bilirubin of at least 2-times the upper limit of normal.

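### SAP 6.6 gives two conflicting rules for unscheduled laboratory and vital-sign values, and no section says which rule governs the per-subject safety counts

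*SAP*

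**What the plan says.** SAP 6.6 contains three rules.

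- Rule 1: laboratory or vital-sign values from visits outside the protocol, or "obtained in the course of investigating or managing adverse events) will be included in listings, but not summaries". The sentence is not limited to by-visit tables.
- Rule 1b: where a visit has several laboratory values, "the observation identified by the investigator to be the scheduled assessment will be used in summaries". This is also unqualified.
- Rule 2, in the next paragraph: "Data from unscheduled assessments will be included in longitudinal data summaries (e.g., minimum, maximum over time". The same paragraph then mentions by-visit summaries as a separate kind of output.

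The outputs at stake are in SAP 5.4. For liver injury, SAP 5.4.4 states that "subjects will be summarized and listed who meet the following criteria". The criteria are "Elevations in either AST or ALT of at least 3-times the upper limit of normal, and" "An accompanying abnormal bilirubin of at least 2-times the upper limit of normal". SAP 5.4.2 and 5.4.3 flag and summarise subjects who meet the Section 10 thresholds for vital signs and laboratory values. SAP 4.2.4 defines a TEAV as a value that is abnormal after dosing and was normal before it.

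Protocol 9.6.2 plans "assessments of change to worst value (to examine worse value, minimum and maximum values are examined". Protocol 7.1.5.2, on potential drug-induced liver injury, adds: "Increases defined above should be confirmed with repeat testing within 48 to 72 hours".

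**The concern.** Rule 1 and Rule 2 give different answers for the same value. A repeat ALT drawn while an adverse event is being investigated is both an extra laboratory value, kept out of summaries, and an unscheduled assessment, included in over-time summaries. The tables that depend on the choice count subjects who ever crossed a threshold. They are the plan's between-arm comparison of rare laboratory and vital-sign abnormalities. If Rule 1 governs them, they can omit a subject whose qualifying value was found because someone looked between visits. If the governing rule is left open, two programmers can both follow the SAP and report different counts, and neither result would be a deviation under SAP 7.

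**Working it through.** The plan states no figure on this point, so there is none to reproduce. The check compares the texts.

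**Step 1. Do the rules overlap?** Rule 1 covers laboratory and vital-sign values from non-protocol visits and adverse-event work-up. Rule 2 covers unscheduled assessments without naming a data type. The Rule 1 values therefore lie inside Rule 2's scope.

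**Step 2. Which rule reaches which table?**

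| Output | Section | Described as a summary | States which draws count | Called longitudinal |
|---|---|---|---|---|
| Section 10 flags, vital signs | SAP 5.4.2 | yes | no | no |
| Section 10 flags, laboratory | SAP 5.4.3 | yes | no | no |
| TEAV counts | SAP 4.2.4, 5.4.3 | yes (SAP 9 lists TEAVs in the laboratory summary) | no; the definition has no scheduled-only limit | no |
| Liver criteria | SAP 5.4.4 | yes | no | no |

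The minimum and maximum in SAP 5.4.2 and 5.4.3 are statistics across subjects at each assessment time. They are not a subject's extremes over time. The only examples that Rule 2 gives therefore match no output described in SAP 5.4. They match the minimum and maximum assessments of protocol 9.6.2, which SAP 5.4 does not mention.

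**Step 3. When do the counts differ?** Let S mean that a subject meets a criterion on at least one scheduled draw, and U that the subject meets it on at least one unscheduled draw in the database. Rule 1 counts S. Rule 2, if it applies, counts S or U. The two differ only for subjects with U and not S.

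Here is an illustration with assumed values, for a subject with normal ALT before dosing:

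- Scheduled draw: ALT 2.6 x ULN, bilirubin 1.7 x ULN. Since 2.6 < 3 and 1.7 < 2, the liver criteria are not met.
- Unscheduled draw: ALT 4.1 x ULN, bilirubin 2.3 x ULN. Since 4.1 ≥ 3 and 2.3 ≥ 2, they are met.
- Liver count: 0 under Rule 1, 1 under Rule 2.
- Section 10 ALT flag (above 3 x ULN): 0 under Rule 1, 1 under Rule 2.
- Section 10 bilirubin flag (above 2.5 x ULN): 0 under both, since 2.3 < 2.5.
- ALT TEAV: 1 under both, because the scheduled value is already abnormal.

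Had the scheduled draw met both liver criteria, the subject would be counted under either rule.

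**Step 4. Can a subject have U and not S?** Yes. Protocol 7.1.5.1 schedules safety laboratory tests at Baseline, Months 3, 6, 9, 12, 15, 18 and 21, and at premature discontinuation. Months 1 and 2 are telephone contacts. On the study days in Table 1 the first gap is 90 − 1 = 89 days, and the later on-treatment gaps are 90 days. A symptom-driven first draw, or an ad hoc repeat of a sub-threshold scheduled value, falls inside such a gap.

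**The case against.** The strongest reply is that the intent can be recovered. The second paragraph of 6.6 separates longitudinal from by-visit summaries, so the natural reading keeps extra values out of by-visit tables and lets them into over-time summaries. The liver and Section 10 counts are per subject and tied to no visit, so they belong with the latter. SAP 1.9 declares only one change from the protocol's statistical section (Bazett's correction), so the worst-value assessments have not been shown to be dropped. All this is fair as to intent. It does not settle the text: Rules 1 and 1b are unqualified, no section classes the per-subject counts as longitudinal, and under protocol 9.0 the SAP supersedes the protocol.

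Three stronger readings are tempting, and the documents do not support them.

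- A reader might infer that the repeat tests of protocol 7.1.5.2 are the values lost. Those repeats are triggered only once AST or ALT is at least 3 x ULN together with bilirubin at least 2 x ULN (with a further doubling from baseline where the transaminase was already raised). If the triggering draw was scheduled, the subject already meets SAP 5.4.4 and is counted. The loss needs a qualifying value that appears only off-schedule.
- A reader might size the loss from visit spacing. If an episode lasts D days and starts at random in a 90-day gap, the chance that no scheduled draw falls inside it is 1 − D/90: 84% for 14 days, 69% for 28, 33% for 60 and 0% for 90. The documents give no episode length, and an episode with no draw at all is seen under no rule. These figures describe the schedule, not the effect of 6.6.
- A reader might infer that a liver signal could vanish. Extra values stay in listings. Protocol 7.1.5.2 has potential liver-injury cases reported as SAEs, and SAP 4.2.1 tabulates SAEs. SAP 5.4.3 summarises potentially significant laboratory abnormalities as TEAEs, and SAP 4.2 has safety listings reviewed by medically qualified staff.

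**Conclusion.** The conflict in SAP 6.6 is real, and the sections that depend on it do not resolve it. Under Rule 1, subjects who meet a TEAV, Section 10 or liver criterion only on an unscheduled draw are left out of the corresponding table; all others are counted the same either way. The consequence is a possible under-count, or a count that varies with the reading, in the laboratory and vital-sign safety tables. With rare events, one subject can change how such a table reads, and listings do not supply proportions by arm. The safeguards above mean that the case itself remains visible elsewhere. Efficacy and alpha are unaffected. The number of subjects affected cannot be derived from the documents: it depends on how often unscheduled draws occur and on what they show. The conclusion rests on the wording alone and assumes that at least some unscheduled values reach the database.

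**What to change.** 1. In SAP 6.6, limit both the first sentence and the sentence on the investigator-identified scheduled value to by-visit summaries.
2. In SAP 5.4.2 to 5.4.4 and Section 10, state that every post-baseline value in the database, scheduled or unscheduled, counts toward the per-subject TEAV, potential-clinical-concern and liver-criteria tables and toward the minimum and maximum assessments of protocol 9.6.2. Describe those assessments in SAP 5.4.
3. Specify the on-treatment window for these counts. SAP 6.2 uses 45 days after the last dose, and SAP 6.5 calls follow-up data unsuitable for statistical analysis. Protocol 9.6.2, by contrast, includes off-treatment and follow-up values in its last-available assessment. These need to be reconciled.
4. Reconcile with SAP 4.2.4, under which laboratory data that the protocol does not require are not captured. Some extra values may never reach the database, and the tables should say so.

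ECG categories can stay as they are on this point, because the excluding sentence names only laboratory data and vital signs.

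The cost is a few sentences in the SAP and one data-selection rule in the programming, with no new data. The downside is that flag counts may rise slightly in both arms. The change should be made before unblinding.
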